4.9 How will the outcome measures be measured at follow-up?

The collection and administration of all outcomes and examinations are standardized and are clearly outlined in the Study Protocol Manual. Surgeons and research assistants will have met on several occasions to discuss and review this protocol.

PRIMARY:

The patients will complete the WORC Score questionnaire pre-operatively and at 3, 6, 12 and 24 months post-operatively. The research assistant, blinded to treatment allocation, will be available to answer any questions. The patient will be examined by the blinded research assistant in a standardized fashion. The surgeon is the last person to examine the patient.

SECONDARY:

The patients will complete the ASES and Constant Score questionnaire pre-operatively and at 3, 6 12 and 24 months post-operatively. The research assistant will be available to answer any questions. The patient will be examined by a blinded assessor in a standardized fashion. The surgeon is the last person to examine the patient and is blinded to the results of the outcomes.

The interpretation of the high-resolution ultrasound is based on healing status and will be carried out by a trained MSK radiologist. Healing status will be documented at both 6 and 24 months as either completely healed, partially healed, or not healed. For tendons partially healed or not healed, the size of the defect will be compared with the size of the tear pre-operatively.

The quantitative T1-MRI will be interpreted by a trained MSK radiologist.

Analysis of the healing matrix will be carried out as described above.

4.10 What is the proposed sample size and what is the justification for the assumptions underlying the power calculations?

The sample size calculation was based on a scale score of 71.31 and standard deviation of 30.43. The authors are assuming superiority from historical controls. Superiority would be considered a difference of more than 30%, or 21.4 points on the WORC scale, from the expected mean. With alpha at 0.05 and power 0.80, the sample size was determined at 33 per group. With a foreseen dropout rate of 25%, we would therefore seek 45 patients per group.

We have experienced a much higher than anticipated rate of withdrawal (~50%) which has mainly been due to 'loss to follow up', or being excluded at the time of surgery, in particular, there has been a large number of participants who signed the consent and completed baseline measures, but never booked a surgery, were not available for the pre-operative trephination procedure, or withdrew consent prior to randomization. Given that we require a sample size of 90 participants who have been randomized *and* received the intervention, we would like to recruit up to 180 participants, however, recruitment will be ceased once 90 participants have been randomized and received the pre-operative intervention.

4.11 What is the planned recruitment rate?

With two surgeons enrolling patients, we plan to recruit 60 patients per year. Recruitment will be completed in a 18 month time-frame. This recruitment rate is expected based on two previous RCT studies conducted at our center with a similar patient population.

4.12 Are there likely to be any problems with compliance?

This being a surgical trial, there is no opportunity for patients to avoid complying with their assigned intervention. It is unlikely that any crossovers would occur from one surgical treatment to the other. It is also unlikely that conversion to open surgery will occur based on the surgeons' previous experience with this procedure and patient population.

4.13 What is the likely rate of loss to follow-up?

Patients are called by the research assistant two to four days before their appointment. Patients will normally reside within 90 minutes traveling time of their surgical centre. Patients who do not attend their appointment are rescheduled. If the patient misses their re-booking then the surgeon will phone the patient to encourage their attendance. In the event that a patient chooses not to return for a follow-up, the questionnaires are mailed out with a stamped return envelope. Patients that can no longer be followed by their original surgeon may be followed at another collaborating center. Research assistants in both cities will communicate to arrange follow-up appointments and maintain contact with the patient.

It has been our experience that these patients are compliant with their clinic follow-ups. The sample size calculation takes into account a 10% loss to follow-up rate. Every effort will be made to minimize this occurrence.

4.14 Details of planned analyses

Primary:

Primary analyses involve a comparison of the mean WORC scores with control data from patients who have undergone an arthroscopic cuff repair, without trephination, obtained through our prospective database. This analysis is a two-tailed unpaired t-test to assess whether there is a statistically significant difference between groups for the mean WORC scores at all time points. The 5% significance level is employed. The underlying assumption for the WORC score data is that there is a normal distribution. If the sample distribution is determined to depart from normal, then a Wilcoxon rank sum test will be performed.

Secondary:

Similar analysis will be carried out for the functional outcome scores. The ASES, Constant Score, and U/S healing rates will be analyzed for differences at 24 months. The planned secondary analyses are performed using a 5% significance level. The secondary outcomes will be analyzed using appropriate statistics; t-tests for continuous and chi-square for dichotomous variables.

Interpretation of the MRI data will involve a comparison of the quantitative T1 signal intensity.

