4.3 Proposed practical arrangements for allocating participants to trial

A treatment allocation schedule will be produced under the supervision of the orthopedic research study coordinator. Allocation to either bone trephination or soft tissue trephination will occur in blocks of 10 in a randomized fashion. Treatment allocation will be determined when the patient is scheduled for surgery. Treatment allocation will be stratified by surgeon.

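### The planned 24-month WORC test uses only patients with a 24-month score; one repeated-measures model would also use the 3-, 6- and 12-month scores and guard against dropout that differs between groups

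*Combined protocol and SAP*

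**What the plan says.** The schedule for the primary outcome is in section 4.9: "The patients will complete the WORC Score questionnaire pre-operatively and at 3, 6, 12 and 24 months post-operatively". Section 4.7 makes 24 months the primary evaluation.

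The analysis is in section 4.14: "This analysis is a two-tailed unpaired t-test to assess whether there is a statistically significant difference between groups for the mean WORC scores". The sentence goes on to cover every time point, so each visit has its own test, with a Wilcoxon rank sum test as the fallback. Section 4.14 names no analysis set, imputation, model across visits, baseline adjustment or sensitivity analysis for missing scores.

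On losses, section 4.10 says: "With a foreseen dropout rate of 25%, we would therefore seek 45 patients per group". Section 4.13 says that the sample size allows for 10%. Section 4.13 also lists reminder calls, rebooking, a call from the surgeon, mailed questionnaires and follow-up at another centre.

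The comparator is not consistent. The primary research question and the null hypothesis in section 4 set bone against soft tissue trephination. Section 4.14 compares with database patients repaired without trephination.

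**The concern.** A two-sample test at 24 months has no place for a patient whose last WORC was at 12 months. That patient counts in the separate tests at the earlier visits but adds nothing to the primary estimate, although a 12-month score says a good deal about the likely 24-month score.

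Two things are at stake. The first is precision in a small trial. The second is bias. If the patients who stop attending differ in earlier WORC, and differ in another way in the other group, the groups left at 24 months are no longer comparable. Leaving the method open also allows it to be chosen after the data are seen.

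**Working it through.** **Inputs from the plan.** Mean 71.31 and SD 30.43 ("The sample size calculation was based on a scale score of 71.31 and standard deviation of 30.43"); difference 21.4 points (0.30 × 71.31 = 21.39); alpha 0.05 and power 0.80; two-sided unpaired t-test; 45 per group; dropout 25% (section 4.10) or 10% (section 4.13).

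**Inputs assumed, because the documents do not give them.** The correlation ρ between 12- and 24-month WORC, the dropout patterns, and that patients who drop out have a 12-month score.

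**1. The plan's own figures.** n = 2(1.960 + 0.842)² × 30.43² / 21.4² = 31.7, so 32 by the normal approximation. The exact t calculation gives 33 (power 0.803), as stated: "With alpha at 0.05 and power 0.80, the sample size was determined at 33 per group". For dropout, 33/0.75 = 44, close to the stated 45, whereas 33/0.90 gives 37. So 45 fits the 25% rate and not the 10% rate.

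**2. Who is left at 24 months.**
- At 25%: 45 × 0.75 = 33.75 per group; 90 × 0.25 = 22.5 patients without a score.
- At 10%: 45 × 0.90 = 40.5 per group; 90 × 0.10 = 9 without a score.

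Both leave at least the 33 required, so power is preserved.

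**3. Precision.** If a fraction m lacks the 24-month score but has the 12-month score, the variance of a likelihood estimate relative to the completers' mean is 1 − mρ².
- m = 0.25, ρ = 0.5: 1 − 0.0625 = 0.94. Effective n is 33.75/0.9375 = 36.
- m = 0.25, ρ = 0.8: 1 − 0.16 = 0.84. Effective n is 33.75/0.84 = 40.2.
- m = 0.10: reductions of 2.5% and 6.4%.

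At 25%, power for 21.4 points rises from 81% to between 84% and 88%.

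**4. Bias with no true difference.** Suppose one arm loses 33% of patients below its median 12-month WORC and 17% of those above (25% overall), and the other arm loses 25% at random. Under normality the two halves lie 0.798 SD either side of the mean. The 12-month mean of those who stay shifts by 0.798 × (0.83 − 0.67)/1.50 × 30.43 = 2.59 points. The shift at 24 months is ρ times this.
- One arm only: 2.59 × 0.5 = 1.3 to 2.59 × 0.8 = 2.1 points.
- Opposite patterns in the two arms: twice that, 2.6 to 4.1 points.
- Same pattern in both arms: the shifts cancel, so about zero.
- At 10% loss in the same proportions (13.2% and 6.8%): 0.798 × (0.932 − 0.868)/1.80 × 30.43 = 0.86, giving 0.4 to 0.7 points in one arm and 0.9 to 1.4 with opposite patterns.

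The standard error at 25% loss is 30.43 × √(2/33.75) = 7.4 points. A bias of 4.1 is 0.55 standard errors and lifts the type I error from 5% to about 8-9%.

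**5. Simulation with a steeper rule.** There were 45 per group, 25% dropout, equal correlations of 0.3 to 0.7 between visits, and dropout odds multiplied by e for each SD of lower 12-month WORC. The completers' t-test was biased by about 1.9 to 4.7 points when the rule acted in one group, and by 3.7 to 9.0 when the rules were opposite. With the same rule in both groups the bias was about zero under no effect. At a true effect of 21.4 points it was 1.1 to 2.1 points toward no difference, because the earlier course then differs between groups. An estimate using baseline and the earlier visits stayed within about 0.3 points of the truth throughout. That last result is partly built in, because dropout was made to depend only on an observed 12-month score.

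**The case against.** Much can be said for the plan, and part of it stands.

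- **Completers-only is nowhere stated.** True; it follows from the named tests and from silence on missing data.
- **The earlier scores are analysed.** True; each visit is tested. A reader might infer that a quarter of patients' data are thrown away. The documents do not support that: the earlier scores are unused only for the 24-month estimate, and the quarter rests on the higher of two conflicting rates.
- **Follow-up is actively pursued.** WORC is completed by the patient, so a mailed form can recover it from someone who does not return. This may reduce the gap but does not say how the remaining gap is analysed.
- **Dropout should be alike in the two arms.** Patients and assessors are blinded (section 4.4) and post-operative care is the same in both groups (section 4.2). A reader might infer that dropout following earlier WORC always biases the comparison. It does not: with the same pattern and no true effect, the bias is about zero. Nothing in the documents shows that patterns will differ between the randomised arms.
- **Power is safe.** This stands in full.
- **The 50% withdrawal.** A reader might infer that half the cohort will be missing at 24 months. Section 4.10 describes this loss as largely before randomisation or treatment, and the target of 90 counts patients randomised and treated.
- **The database controls.** The documents do not say at which visits controls completed WORC or how they were followed. A repeated-measures model cannot be assumed to be available for that comparison.

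**Conclusion.** The concern holds in a limited form. The named 24-month test cannot use about 22 of 90 patients at 25% loss, or 9 of 90 at 10%, although earlier WORC scores may be in hand for them. The sample size is not called into question.

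The avoidable loss of precision is about 6-16% of the variance at 25% dropout, if ρ is 0.5 to 0.8 and the patients lost have a 12-month score. The possible bias is about 1.3 to 4.1 points for moderate patterns specific to one arm or opposite in the two, against a planned difference of 21.4. It is smaller at 10% loss and larger under steeper patterns. It needs dropout related to earlier WORC, or the earlier WORC course itself, to differ between groups. All these sizes rest on assumed correlations and dropout patterns.

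The change should be made because it is cheap and fixes the method in advance, not because the planned comparison is shown to be biased.

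**What to change.** For the randomised bone versus soft tissue comparison, make the primary analysis one mixed model for repeated measures:

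- Outcome: WORC at 3, 6, 12 and 24 months.
- Terms: arm, visit, arm-by-visit, baseline WORC and surgeon (the stratification factor in section 4.3), with unstructured covariance.
- Patients: all randomised patients with at least one post-operative WORC, in the arm to which they were allocated.
- Primary result: the arm contrast at 24 months.
- Sensitivity: one analysis in which missing 24-month values are made progressively worse in one arm, reporting where the conclusion changes.

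Apply the model to the database-control comparison only if the controls have WORC at the same visits, and state whether they do. Reconcile the 25% in section 4.10 with the 10% in section 4.13.

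The cost is new wording in section 4.14 and slightly more analysis work. The randomised arms need no new patients, visits or data. The model relies on scores being missing at random given the observed WORC, which the sensitivity analysis probes, and it does not help patients with no post-operative score.

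### The WORC test in section 4.14 uses neither the pre-operative WORC nor the surgeon stratum, and does not repeat that 24 months is the primary time point

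*Combined protocol and SAP*

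**What the plan says.** Section 4.14 describes the primary analysis as a "two-tailed unpaired t-test to assess whether there is a statistically significant difference between groups for the mean WORC scores at all time points", at the 5% level. The fallback reads: "If the sample distribution is determined to depart from normal, then a Wilcoxon rank sum test will be performed". No covariate, stratification term or baseline adjustment is mentioned. Within 4.14, 24 months is attached only to the secondary outcomes.

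Elsewhere the protocol collects the variables that the analysis leaves out:

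- Section 4.9: "The patients will complete the WORC Score questionnaire pre-operatively and at 3, 6, 12 and 24 months post-operatively". The same schedule holds for the secondary scores: "The patients will complete the ASES and Constant Score questionnaire pre-operatively and at 3, 6 12 and 24 months post-operatively".
- Sections 4.1 and 4.3 stratify the allocation by surgeon (two surgeons).
- Section 4.3: "Treatment allocation will be determined when the patient is scheduled for surgery". Section 4.10 describes "participants who signed the consent and completed baseline measures, but never booked a surgery".

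The objective (section 1), the primary research question and null hypothesis (section 4) and section 4.7 all make 24 months the primary time point. Section 4.16 times the analysis there.

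The comparator also differs between sections. Section 4.14 opens: "Primary analyses involve a comparison of the mean WORC scores with control data from patients who have undergone an arthroscopic cuff repair", meaning patients from a database who had no trephination. The primary research question and null hypothesis in section 4 compare the two randomised arms.

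**The concern.** In a small randomised trial, a baseline measurement of the outcome is usually the cheapest source of precision, and a factor used to stratify the allocation normally belongs in the analysis. This plan collects the first and stratifies on the second, then uses neither. The baseline score appears to be a proper covariate: some patients had completed baseline measures without ever booking surgery, and allocation is made when surgery is scheduled, so baseline seems to precede allocation.

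The Wilcoxon fallback has the same gap. It would be chosen after looking at the data, under a trigger that is not defined. It ignores both variables and gives no difference in means, although section 4.10 states the target effect in WORC points.

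A smaller matter is that 4.14, read alone, tests every visit at 5% without saying which one decides. The rest of the protocol settles this, but the analysis section should say so too.

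At stake are a wider interval than the data allow, a slightly conservative test if the surgeons' outcomes differ, and some room to present another visit as the main result.

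**Working it through.** **Inputs.** SD 30.43, difference 21.4 points, two-sided alpha 0.05, power 0.80 and 33 per group come from section 4.10. The difference is 30% of the expected mean: 0.30 × 71.31 = 21.39. The correlation r between pre-operative and 24-month WORC, and the share p of WORC variance explained by surgeon, are not in the documents. Both are assumed and shown as ranges. All figures are for the randomised bone-versus-soft contrast and assume normal data.

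**Step 1: the plan's own figure.** For an unadjusted two-sided t-test with n = 33 per arm (64 degrees of freedom), SE = 30.43 × √(2/33) = 7.491. The noncentral t distribution gives power 0.803 at 21.4 points. With n = 32 it gives 0.791, so 33 per group is reproduced. The sample size therefore rests on one unadjusted test.

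**Step 2: unadjusted precision.** Half-width of the 95% interval = 1.998 × 7.491 = 14.97 points.

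**Step 3: ANCOVA with baseline WORC and surgeon** (62 degrees of freedom):

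SE = 30.43 × √(1 − r²) × √(2/33) × √(1 + 1/61)

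The last term is the average cost of chance baseline imbalance. At r = 0.5, SE = 6.541 and the half-width is 1.999 × 6.541 = 13.07. The equivalent unadjusted size is 33 / [(1 − r²)(1 + 1/61)] per arm. The power column also assumes that 21.4 points, which 4.10 sets against historical controls, applies to bone versus soft. The other columns need no assumed effect.

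| r (assumed) | Half-width, points | Equivalent unadjusted n per arm | Power at 21.4 |
|---|---|---|---|
| Unadjusted | 14.97 | 33 | 0.803 |
| 0 | 15.10 | 32.5 | 0.797 |
| 0.1 | 15.02 | 32.8 | 0.801 |
| 0.2 | 14.79 | 33.8 | 0.812 |
| 0.3 | 14.40 | 35.7 | 0.832 |
| 0.4 | 13.84 | 38.7 | 0.861 |
| 0.5 | 13.07 | 43.3 | 0.896 |
| 0.6 | 12.08 | 50.7 | 0.937 |

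The break-even correlation is about 0.13. Simulations with both covariates fitted (40,000 runs each) gave ANCOVA power of 0.796, 0.833, 0.898 and 0.935 at r = 0, 0.3, 0.5 and 0.6, in line with the formula.

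**Step 4: a larger evaluable number.** Section 4.13 states 10% loss, where 4.10 states 25%. With 45 per arm and 10% loss, about 40 remain (45 × 0.90 = 40.5). The unadjusted half-width is then 13.55 and power 0.874. At r = 0.3 with ANCOVA they are 13.01 and 0.899.

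**Step 5: omitting surgeon.** If surgeon is balanced across arms and explains a share p of the variance, the unadjusted test overstates its standard error. Its true error rate is 2 × P(T₆₄ > 1.998 / √(1 − p)), which is 4.8% at p = 0.02 and 3.9% at p = 0.10. Simulation at r = 0.3 gave 4.8% and 3.8% unadjusted, and 5.0% in both cases with surgeon in the model.

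**The case against.** The strongest reply is that the quoted test is not the one quantified above. As written, 4.14 compares trephined patients with non-randomised database controls, and 4.10 says "The authors are assuming superiority from historical controls". For that comparison surgeon is not a randomisation stratum, and missing baseline adjustment is a question of confounding. This stands. The comparator conflict is the larger defect in the paragraph and must be settled first. It does not remove the present point: settling it means rewriting 4.14, and the rewrite could otherwise keep the same unadjusted test for the randomised contrast.

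It can also be said that no error is shown, since the unadjusted test is valid and matches the sample size. That is true, and the point is an improvement in efficiency.

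The benefit depends on a correlation the documents do not give. At r = 0.3 the half-width falls by only about 0.6 points, and substantial gains need r near 0.5. The surgeon share is likewise assumed, and could be small with two fellowship-trained surgeons using a standardised technique. These limits stand, but the risk is one-sided: at worst 0.7 percentage points of power are lost (0.803 to 0.797), against about 9 gained at r = 0.5. At 40 per arm the gain at r = 0.3 is 2.5 points instead of 2.9, so it shrinks but remains.

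The fallback test is pre-specified, and the calculations here assume normality, so they do not show that ANCOVA beats a rank test on skewed scores. The case for demoting the Wilcoxon test rests on fixing the quantity to be estimated in advance, not on power.

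Finally, 24 months is already primary in several sections. Agreed: that part is a clarification, and no inflation of type I error is claimed.

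**Conclusion.** The point holds as a recommended improvement. For the randomised contrast, the planned test is valid but gives up precision from data the trial already collects. At 33 per arm the expected half-width of 15.0 points would be about 14.4 at r = 0.3 and 13.1 at r = 0.5, equal to unadjusted trials of about 36 and 43 per arm. Below r of about 0.13 there is nothing to gain and very little to lose. Leaving out surgeon makes the test slightly conservative, with a true error of about 4.8% to 3.9% if surgeon explains 2% to 10% of the variance.

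These sizes rest on the planning SD of 30.43 and on assumed values of r and p. The power figures rest further on carrying 21.4 points over to bone versus soft. None of this extends to the database comparison in 4.14. With 24 months decisive, as the rest of the protocol says, type I error is held at 5%, and 4.14 needs only a sentence to say so.

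**What to change.** First reconcile the comparator in 4.14 with the bone-versus-soft question and null hypothesis in section 4. Then replace the primary paragraph with wording such as:

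> The primary analysis is the bone-minus-soft difference in mean WORC at 24 months with its 95% confidence interval, from an ANCOVA with baseline WORC and surgeon as covariates, tested two-sided at 5%. Contrasts at 3, 6 and 12 months are secondary. The Wilcoxon rank sum test is a sensitivity analysis only.

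Use the same model for ASES and Constant, each with its own pre-operative score. A repeated-measures mixed model with the same covariates may be added as a further sensitivity analysis.

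The cost is a change of wording and slightly more analysis work. For trial patients, the baseline scores and surgeon are already recorded, so no new data are needed. The documents do not say whether the database controls have these variables, and this proposal does not cover that comparison.

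### The primary WORC test can change from a comparison of means to a Wilcoxon test on an unstated criterion, although the trial is sized and superiority is defined on a difference in means

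*Combined protocol and SAP*

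**What the plan says.** Section 4.14 (Primary) states: "This analysis is a two-tailed unpaired t-test to assess whether there is a statistically significant difference between groups for the mean WORC scores". The level is set by "The 5% significance level is employed". It continues "The underlying assumption for the WORC score data is that there is a normal distribution", and then "If the sample distribution is determined to depart from normal, then a Wilcoxon rank sum test will be performed". It does not say which normality test or plot is used, at what threshold, in which group or visit, when, or by whom. It names no effect measure to accompany a Wilcoxon result. The comparison group is database patients repaired without trephination, whose number is not given.

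Section 4.10 works only in means. Its planning values are given as "The sample size calculation was based on a scale score of 71.31 and standard deviation of 30.43". The margin is put on the same scale: "Superiority would be considered a difference of more than 30%, or 21.4 points on the WORC scale, from the expected mean". From these, at 80% power and a 5% level, the section derives 33 patients in each group, raised to 45 to allow for 25% dropout.

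Section 4.7 places the primary evaluation at 24 months. For the functional scores, 4.14 says the analysis will be similar and then names t-tests for continuous outcomes, so it is unclear whether the Wilcoxon fallback applies to ASES and Constant.

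**The concern.** The two tests answer different questions. The t-test compares means, which is what 4.10 plans for and what 4.14 says it is testing. The Wilcoxon test compares whole distributions and gives no difference in points, so its result cannot be set against the 21.4-point superiority margin. Which question the trial answers would be settled after the outcome data are seen, by a rule that is not written down.

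Two consequences follow. A significant primary result could arise from a difference in spread or shape while the means are equal, and then be reported as a difference in mean WORC. Conversely, a true difference in means could be missed by the rank test when a test of means would find it.

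**Working it through.** **1. The plan's own size.** Inputs from 4.10: difference 21.4 (0.30 × 71.31 = 21.39), SD 30.43, two-sided alpha 0.05, power 0.80.

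n = 2 × [30.43 × (1.960 + 0.842) / 21.4]² = 31.7 per group by the normal approximation. The exact noncentral-t calculation gives 32.73, so 33, with power 80.3%. The stated figure reproduces. Dropout: 33 / 0.75 = 44, against the stated 45.

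**2. What a Wilcoxon size would be.** For a pure location shift, divide by the asymptotic relative efficiency. Normal data: 32.73 / 0.955 = 34.3, so 35. Worst case: 32.73 / 0.864 = 37.9, so 38.

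**3. Do the planning figures fit a normal curve?** The documents do not give the WORC range, so 0-100 is assumed here.
- Distance from mean to ceiling: (100 − 71.31) / 30.43 = 0.94 SD. A normal curve would put 17% of scores above 100.
- Target mean: 71.31 + 21.4 = 92.71. The largest SD possible there is √(92.71 × 7.29) = 26.0, below the planned 30.43.

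**4. How often would the switch fire?** Scores are simulated from beta distributions on 0-100, matched to mean and SD, with 33 per group. The trigger is assumed to be Shapiro-Wilk p < 0.05 in either group, since the plan names none. Both groups have mean 71.31 and the same SD.

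| SD | Switch fires | Rule rejects |
|---|---|---|
| 30.43 | 100% | 4.9% |
| 25 | 99% | 5.1% |
| 20 | 83% | 5.1% |
| 15 | 45% | 5.1% |

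With unbounded normal data the switch fires in about 9%. When the distributions are identical, the rule holds 5%.

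**5. Equal means, different spread, 33 per group.**

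| Means | SDs | Switch rule rejects | t-test rejects |
|---|---|---|---|
| 71.31 | 30.43 v 25 | about 9% | 5-6% |
| 71.31 | 30.43 v 20 | about 18% | 5-6% |
| 80 | 25 v 15 | about 33% | 5-6% |
| 71.31 | 20 v 15 | about 7% | about 5% |
| 71.31 | 22 v 20 | about 5-6% | about 5% |

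The switch-rule rates come from at least 3,000 trials; for a rate of 18% the simulation standard error is √(0.18 × 0.82 / 3000) = 0.7 percentage points. At 45 per group the first two rates rise to about 11% and 22%.

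**6. Unequal group sizes.** The number of database controls is unknown. Take 33 trial patients (SD 20) against 100 or 200 controls (SD 30.43), with equal means. The switch rule rejects in 21% and 20%, the pooled t-test in 1.8% and 0.8%, and Welch in 5.1% and 5.3%. A test of means should therefore be Welch, not pooled.

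**7. Power, 33 per group, means 71.31 (SD 30.43) v 92.71.**

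| Second SD | Test of means | Wilcoxon |
|---|---|---|
| 15 | 96% | 99% |
| 10 | 99% | 83% |
| 7 | 99% | 63% |

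With unbounded normal data and SD 30.43 in both groups, the figures are 80% and 78%.

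**The case against.** A t-test with a rank-test fallback is a common convention, and naming the fallback in advance limits the freedom to choose. The rule does not inflate type I error when the groups have the same distribution, so a reader who infers a general inflation goes beyond the evidence.

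In the scenarios with high rejection rates the distributions do differ, and so do the medians (83.7 v 78.1, 83.7 v 75.0, and 91.8 v 83.3). The null hypothesis in section 4 is no difference in quality-of-life outcome, not equality of means. A Wilcoxon rejection in those cases is therefore wrong only as a statement about mean WORC. The scenarios are also demanding: a beta distribution with mean 71.31 and SD 30.43 is U-shaped, with a third of patients above 95, and no document gives that shape.

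All of this stands and limits the size of the point. It does not remove it. Section 4.14 states its test in terms of mean WORC and 4.10 defines superiority in points, so the rank test leaves the plan's own question unanswered. Differences in spread cannot be dismissed when the comparison group is not randomised.

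**Conclusion.** The point holds as a cheap improvement. The plan leaves open which primary test will be used and what effect will be reported, and the fallback does not estimate the quantity on which the trial was sized. With equal means and clearly different spread, the rule rejects in about 9% to 33% of simulated trials instead of 5-6%; with mild differences, about 5-7%; with identical distributions, 5%. These figures rest on an assumed 0-100 range, beta-shaped scores and Shapiro-Wilk at 5% in either group.

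Two stronger readings are tempting and are not supported:
- **That the t-test will almost certainly be abandoned.** This is very likely on a 0-100 scale with SD near 30, but about an even chance at SD 15. It also depends on a criterion the plan does not state; a plot or a pooled check could give a different answer.
- **That the sample size is therefore wrong.** The 33 per group is correct for the t-test, and a Wilcoxon size for a location shift would be only 35 to 38.

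**What to change.** In 4.14, name one primary analysis whatever the shape of the data: the difference in mean 24-month WORC with a 95% confidence interval, by Welch t-test or by a baseline-adjusted linear model with robust standard errors. Delete the switch. Report the Wilcoxon test as a sensitivity analysis. State that the same rule applies to ASES and Constant.

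The cost is a few sentences of wording, to be settled before outcome data are examined; the sample size does not change. The effect on power depends on shape. In the simulated cases it ranges from a small loss (96% v 99% when the second SD is 15) to a considerable gain (99% v 63% when it is 7).
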